4.2.2 Secondary Outcome Measures

Secondary outcomes include:

- Code status preferences (Aim 1)
- Use of palliative care consult/services (Aim 1)
- Hospice use (Aim 1)
- Health Care Proxy (Aim 1)

Secondary outcomes related to Aim 2a (patients 18+ years admitted to one of the study inpatient units with ADRD/delirium) include:

- Documentation of ACP Preferences in Electronic Health Record

Secondary outcomes related to Aim 2b (caregivers of patients with ADRD/Delirium) include:

- ACP knowledge (Aim 2)
- Confidence in future care (Aim 2)
- Communication satisfaction (Aim 2)
- Decisional satisfaction (Aim 2)
- Decisional conflict (Aim 2)

5 Study Design

This is pragmatic SW-CRT of a PCE-led, video-assisted COVID-19 ACP intervention in inpatient-based units (3 medical-surgical wards, Medical ICU, Cardiac ICU, Neurology ICU, step-down unit) at two hospitals: BMC and North Shore University Hospital (Northwell Health). All inpatients ≥ 65 and all patients with ADRD/Delirium ≥ 18 who are hospitalized on a unit during the intervention phase will receive the intervention.

This 2-year study (2 month data collection and tool preparation, staff training and site standardization (we are already embedded in both health systems doing similar work; thus this

short timeframe is feasible); 16 months rolling recruitment and surveying; 2 months data cleaning and analysis, and 4 months manuscript preparation and dissemination of findings) will roll out the intervention to 14 randomized inpatient units at 2 sites. Every two months, an additional inpatient unit will be added to our intervention at each hospital, i.e., there will be seven waves or "steps"; for a total of 7 units at each hospital.

Consistent with a SW-CRT with two hospital units per step (cluster), prior to the collection of any data in the pre-intervention period, we will generate a set of uniform random numbers for each of the seven clusters to be assigned to a starting period for the study intervention. There will be eight study periods in total with a usual care period at the start of the study for all clusters. The first randomized intervention period will then begin in period two.

Cluster	Baseline	14 Months of Clustered Intervention Expansion							
	M0	M2	M4	M6	M8	M10	M12	M14	
1									
2									
3									
4									
5									
6									
7									

The data needed to assess the outcomes for all patients will be derived from each hospital's EHR (Aim 1).

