12.2 Sample Size Determination

Statistical power and sample size: All sample size estimates here assume a minimum of 80% power and a two-sided alpha of 0.05. We employ the method for the computation of sample size for cross-sectional stepped wedge studies comparing intervention to usual care in two-group statistical analyses. This method incorporates information on the number of steps used in the

stepped wedge/cluster randomized design, the number of subjects per time period, and the degree of clustering via the intraclass correlation coefficient (ICC) to compute the design effect, the factor by which the sample size found to provide sufficient statistical power for a meaningful intervention difference in outcome assuming independent data is multiplied. For the primary outcome of the documentation of ACP in the medical record, a sample size of 440 records per group in a chi-squared test for independent data will provide 80% power at a two-sided alpha of 0.05 to detect a difference in the proportion of subjects with notation of 35% in the intervention group compared to 25% in the usual care group, values consistent with prior research and expectation based on clinical data from the two health systems estimated from recent data. Based on our planned number of steps (7 with one uniformly applied usual care period across all hospital units), enrollment per study period, and a reasonable ICC of 0.01, the design effect is 2.72. Thus, we will need to obtain outcome data from the records of at least 2394 subjects overall (1197 per health system) to provide 80% power for our analysis of intervention effectiveness. We anticipate, however, that as many as 15,000 records will be available for analysis with respect to the documentation of ACP. Thus, our planned sample size for our primary records-based analysis on 15,000 records will therefore provide more than adequate power to test for differences in our primary outcome.

Data for Aim 1 is derived from the EHR and as is typical for trials that integrate new initiatives within the workflow of large institutions in a SW-CRT that does not involve consent. Indeed, we have been previously approved by multiple IRBs for such activities. Along with our exceedingly efficient NLP-assisted and human-confirmed software method for EHR data extraction, we can have a very large study sample with for this activity.

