Primary outcome: ACP documentation. In order to formally estimate and test differences in the proportion of patients with documentation of ACP between the intervention and usual care groups, we will employ logistic regression models for correlated binary outcome data. These models will either involve the use of robust variance methods to account for the clustering of these data by hospital site and/or health system via generalized estimating equations (GEE) or the inclusion of a random effects terms (in which case, the results will be interpreted as cluster-specific). Other potential modifiers of the effect of intervention, confounding variables, or covariates can be added to this model as fixed effects. Although we do not expect effect modification in the study data, we will examine the potential for such effects (interaction) through the use of stratified analyses and the inclusion of interaction terms with study group in our statistical models. Candidate effect modifiers will be specified a priori and will include age, gender, race/ethnicity, religion, and language. We will also examine and incorporate secular trend effects, i.e., the effect of time over the course of the study. Statistically significant interactions with the intervention will be retained and the nature of heterogeneous intervention effects will be estimated using the interaction model.

Based on our prior work in which we exhibited the fact that African-American and Hispanic patients are at particularly high risk for lower level of knowledge related to ACP, not discussing ACP with family, not having a health care proxy, and not having ACP documentation, we anticipate that this intervention may be particularly beneficial for African-American and Hispanic patients.(115, 131, 132) Accordingly, we will evaluate heterogeneous treatment effects by race and ethnicity and anticipate having adequate diversity in our study population to make such assessments. All data regarding Aim 1 will come from the EHR. Our institutions maintain excellent self-report information regarding race and ethnicity.

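### One permitted form of the primary GEE clusters by hospital or health system with no stated working correlation, and so does not match the unit-level model behind the 2.72 design effect

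*Combined protocol and SAP*

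**What the plan says.** Section 12.3 (Aim 1, primary outcome) offers two forms of logistic model. For the first it says: "These models will either involve the use of robust variance methods to account for the clustering of these data". The sentence then gives the clustering level as hospital site and/or health system, fitted by GEE. The second form has random effects, and their level is not stated. No working correlation is named, and no unit term is specified. Covariates may be added but need not be.

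On time, the section says: "We will also examine and incorporate secular trend effects, i.e., the effect of time over the course of the study". It does not say whether time is categorical or whether it may differ by hospital.

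Earlier in Section 12.3, the general text says that health system and hospital unit will both be examined as clustering variables, with the unit as the primary one.

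Section 12.2 sizes the trial with a stepped-wedge design effect: "a reasonable ICC of 0.01, the design effect is 2.72". It derives a minimum of 2,394 records and expects up to 15,000. Section 5 describes 14 units (wards, three kinds of ICU, step-down) in two hospitals. Every two months "an additional inpatient unit will be added to our intervention at each hospital".

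**The concern.** In a stepped wedge, the treatment effect can be estimated from two sources: each unit's change when it crosses over, and the contrast between treated and untreated units in the same period. The design effect in Section 12.2 belongs to an analysis that weights these two sources by their precision, so it relies mainly on the first. A GEE with independence correlation, or with correlation only at hospital level, gives the between-unit contrast a fixed large weight however much units differ. Robust variance then reports the resulting imprecision honestly but does not remove it.

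The options that Section 12.3 permits can therefore differ severalfold in standard error, and the choice among them is left open. What is at stake is precision. Section 12.2 argues that effect sizes matter more than p-values, and it relies on the large sample for less common outcomes and for subgroups as small as 20% of the population.

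**Working it through.** **The plan's own figures.** The standard cross-sectional stepped-wedge design effect with k = 7 steps, one baseline period, one measurement per step and n subjects per cluster-period is

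8 × [1 + ρ(8n − 1)] / [1 + ρ(4.5n − 1)] × 3(1 − ρ) / [2(k − 1/k)].

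The plan does not state n. With ρ = 0.01 and n = 60 this is 8 × (5.79/3.69) × (2.97/13.714) = 2.72, so the stated value is reproduced at about 60 per cluster-period. At 15,000/(14 × 8) = 133.9 per unit-period it is 2.89. The total also follows: 2 × 440 × 2.72 = 2,393.6, or 2,394. Separately, 440 per group is the 90% power size for 25% versus 35% (80% needs 329). That gives extra margin at 2,394.

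**Inputs.** From the plan: 14 units, 8 periods, two units crossing per step (one per hospital), ICC 0.01, 25% versus 35%, and N = 2,394 or 15,000. Assumed: equal unit-period sizes n = N/112, mean rate 30% (variance 0.21), categorical periods, the risk-difference scale, and ICCs above 0.01.

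Let τ² = 0.21ρ be the between-unit variance and s² = 0.21(1 − ρ)/n the variance of a unit-period mean. Let z be the treatment indicator minus its period mean.

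- Total Σz² = 14 × Σ(j/7)(1 − j/7) = 16.
- A unit that crosses at step j has row sum 4 − j, so the squared row sums total 2 × (9 + 4 + 1 + 0 + 1 + 4 + 9) = 56.
- The between-unit part is 56/8 = 7. The within-unit part is 16 − 7 = 9.

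Variance of the treatment effect:

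- Unit random intercept or unit-exchangeable GEE: 1 / [9/s² + 7/(s² + 8τ²)].
- Unit indicators: s²/9.
- Independence GEE: [9s² + 7(s² + 8τ²)] / 16².
- Hospital-level exchangeable GEE: the same as independence, because in every period the two hospitals have the same treated fraction.

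**N = 15,000, ρ = 0.01.** s² = 0.99 × 0.21/133.9 = 0.001552, τ² = 0.0021, and s² + 8τ² = 0.01835.

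- Unit-level: 1/(5,799 + 381) = 0.0001618, SE 1.27 points.
- Unit indicators: 0.001552/9 = 0.0001725, SE 1.31 points.
- Independence: (0.01397 + 0.12845)/256 = 0.000556, SE 2.36 points.

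Divided by the simple two-group variance, 0.84/15,000 = 0.000056, the design effects are 2.9 (unit-level) and 9.9 (independence). The first agrees with the plan's formula at this n, which confirms that the formula describes the unit-level model.

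**All settings.** Power for 10 points is Φ(0.10/SE − 1.96). The ratio is to the unit-level SE at ICC 0.01 for the same N.

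| Records | ICC | Unit-level SE | Independence or hospital-level SE | Ratio | Power of the latter |
|---|---|---|---|---|---|
| 15,000 | 0.01 | 1.27 | 2.36 | 1.85 | 99% |
| 15,000 | 0.02 (assumed) | 1.28 | 3.19 | 2.5 | 88% |
| 15,000 | 0.03 (assumed) | 1.29 | 3.84 | 3.0 | 74% |
| 15,000 | 0.05 (assumed) | 1.28 | 4.89 | 3.8 | 53% |
| 2,394 | 0.01 | 2.90 | 3.27 | 1.13 | 86% |
| 2,394 | 0.02 (assumed) | 3.02 | 3.90 | 1.34 | 73% |

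Unit-level power exceeds 99% at 15,000 records. At 2,394 it is 93% (ICC 0.01) and 91% (0.02). ICCs of 0.01, 0.02 and 0.05 imply between-unit SDs, √(0.21ρ), of 4.6, 6.5 and 10.2 points.

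A small logistic-GEE simulation (40 replicates per setting) agreed in direction. With a unit SD of 0.5 on the logit scale, the empirical SD of the treatment coefficient was 0.21 with independence, 0.067 with unit-exchangeable correlation and 0.071 with unit indicators.

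**Hospital-specific time.** With equal sizes, hospital-by-period shocks leave the true SE ratios unchanged (1.85 and 1.00). With unequal sizes and an assumed shock variance of 1% of the total, the unit-exchangeable ratio has a median of about 1.06. What changes is the reported SE. With one common period effect, the unit-clustered robust SE under exchangeable correlation is expected to be 1.06 to 1.9 times the reference for assumed shock variances of 0.1% to 2% of the total. That makes it too large. Fitting periods by hospital removes this.

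**The case against.** The best defence is that the plan already makes the unit the primary clustering variable, and that hospital site in the model sentence may be loose wording for it. Unit-exchangeable GEE and a unit random intercept are both permitted, and both keep the ratio near 1. The plan nowhere says independence. This stands against any reading that the plan ignores units, but it does not settle the matter. The sentence that defines the primary model names a different level, and even with the unit as cluster an unstated working correlation leaves independence available.

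A reader might infer that the standard error is 2 to 4 times too large on the plan's own terms and that the power claim fails. The documents do not support this. At ICC 0.01 the ratio is 1.13 to 1.85, and power is 86% to 99%, above the 80% claimed. Ratios of 2 or more need a higher ICC, and no unit-level ACP rates are given. Section 12.2 says that units differ in their patient populations, but in the context of cluster size. At 15,000 records, power drops below 80% only when the ratio exceeds about 2.8, which requires an ICC above roughly 0.025.

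Nor does the missing hospital-by-time term drive the loss. Each step adds one unit per hospital, so hospital shocks largely cancel from the estimate.

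The plan's confounding screen and optional covariates might pick up unit type, but neither names it.

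**Conclusion.** The point holds as a mismatch between a permitted primary model and the model used for sample size. A GEE with independence or hospital-level correlation has about 1.85 times the unit-level standard error at 15,000 records and ICC 0.01. That costs precision rather than power (about 99%). The factor is about 2.5 to 3.8 under assumed ICCs of 0.02 to 0.05, with power 88% to 53%. At 2,394 records the margin is thinner: 86% at ICC 0.01 and 73% at an assumed 0.02.

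These figures rest on equal unit-period sizes, a 30% mean rate, normal-approximation power and a unit correlation that is constant over time. If that correlation decays (assumed cluster autocorrelation 0.8), the unit-level model also loses precision. Relative to the same reference, the SEs are then 1.74 against 1.12 at ICC 0.01 and 3.57 against 1.55 at 0.05, so the gap narrows but remains. Hospital-specific time is a secondary matter that concerns the reported SE only.

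**What to change.** In the primary-outcome paragraph of Section 12.3, name one primary model. It should be logistic, with the hospital unit as the cluster, categorical period effects, and one of a unit random intercept, a unit-exchangeable working correlation or unit indicators. Remove GEE with independence correlation, or with clustering at hospital or health-system level, as a primary option. Align the sentence with the general text that already makes the unit primary.

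At 15,000 records the three choices are nearly equivalent (1.27 to 1.31 points at ICC 0.01). Near 2,394 records, unit indicators have no advantage over independence at ICC 0.01: their ratio is also 1.13.

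As a secondary change, fit the period effects separately by hospital. Each hospital is a complete stepped wedge, so this is estimable. It guards the reported SE against hospital-specific time shocks, and in a simulation without shocks the SD of the estimate was 0.0125 with one choice and 0.0123 with the other.

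The cost is SAP wording and, at most, about 20 parameters (13 unit indicators and 7 hospital-by-period terms) against thousands of records.

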7.1 Subject Inclusion Criteria

Over the two years of the trial, we will examine data on approximately 15,000 patients ≥ 65 admitted to these 23* units for our primary and secondary outcomes (Aim 1). Given the pragmatic nature of this trial, our inclusion criteria are quite broad and consistent with the goal of pragmatic trials.

We will also survey caregivers of 600 patients with ADRD/Delirium to conduct a telephone administered survey for caregiver-centered outcomes (knowledge, confidence, communication satisfaction, decisional satisfaction, and decisional conflict) during the index hospitalization. Caregivers may or may not be designated as ADRD/Delirium legal surrogate decision maker for the patient (i.e., most patients with ADRD/Delirium do not have a legally designated representative.) Any adult identified in the EHR as the contact family member or friend will be eligible to partake in the caregiver survey. Half of surveys will be conducted during the control period; half during the intervention period. Caregivers will be either English- or Spanish-speaking adults, which are the languages in which our surveys are validated. For patients in the control group, surveys will be completed during the hospital stay or within 1 week of discharge. For patients in the intervention group, the survey will be completed AFTER the PCE intervention, and up to 1 week after discharge.

*14 units (7 per hospital) will be included in the stepped wedge trial, an additional 9 units (3 at BMC and 6 at NorthShore) will be used to recruit additional control participants only. These additional units were added due to low recruitment at the start of the study and the decreasing number of control units as the stepped wedge design progresses. The target enrollment of 600 caregivers is still accurate.

Adding delirium to the list of eligible diagnoses will also increase the potential number of eligible subjects. The surveys are applicable to the caregiver of any patient who is not capable of making their own health decisions; this includes patients who are experiencing any sort of memory or cognitive decline.

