12.3 Statistical Methods

Statistical Analysis: For the primary analyses of the primary and secondary outcomes, there will be no crossover of data for subjects from usual care to the intervention during the study; that is, subjects will only contribute data once during the course of the study, from their index hospitalization. Similarly, patients who move units during the course of their index hospitalization will be assigned to contribute intervention time data if they spend at least eight daytime weekday hours after being identified as meeting the inclusion criterion on a clinical unit where the intervention is being conducted. Accordingly, data being contributed by patients at each site during the pre-intervention period and data being contributed by patients after the initiation of the intervention will be kept separate for initial analyses. However, because we expect some patients to have multiple hospitalizations during different steps or to different units (i.e., crossover design), we will perform secondary analyses on all outcomes including data from the index hospitalization. This will include stratified sensitivity analyses of patients who contribute data (a) only to control period; (b) only to intervention period; or, (c) to both control and intervention periods.

Given the randomized nature of the stepped wedge design, we will report our results according to CONSORT guidelines. For the aims of the study that require patient/caregiver enrollment (Aim 2), we will record the number of people approached, screened, ineligible, and refusing participation. We will record subject attrition and note all adverse events. We will employ the intent-to-treat principle in our comparative analyses between the intervention and usual care groups. All hypothesis tests will employ a two-sided alpha level of 0.05. Given that the primary aim will be addressed by the analysis of data obtained from available patient records for the study period, we will examine the distributions of relevant variables focusing on the data relating to the documentation of ACP, the outcome of this aim. For the secondary aims of the study that will require enrollment of a caregiver sample for interview (Aim 2), we will examine the

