distributions of the uncertainty and knowledge scale scores, the outcomes of interest between intervention and usual care subjects, as well as the distributional characteristics of all other salient study variables. We will generate descriptive statistics (means, standard deviations, quantiles for continuous variables; counts and percentages for categorical variables) and schematic plots (box-and-whisker, quantile-quantile plots). Given the nature of the cluster randomization that we will employ, we will utilize statistical analytic methods that take the correlated nature of the data into account as well as the influence of time to account for secular trends. In this study, we will examine both the health system and hospital unit as clustering variables, with the hospital unit as the primary clustering variable. We will compare the intervention and usual care groups on salient variables in order to assess balance in the distributions of these variables. Variables found to differ between the study groups will be further evaluated to assess their confounding effects of intervention vs. usual care differences on outcomes in multivariable analyses for correlated (clustered) data.

Aim 1. To test the combined effects of a COVID-19 ACP Educator-led, video-assisted palliative care intervention on rates of: ACP documentation; Medical orders for resuscitation preferences in the EHR; Palliative Care Consults; and, Hospice use. ***Hypothesis: A higher proportion of patients in the intervention phase (vs. control) will: complete ACP documentation (primary trial outcome), have documented orders for resuscitation preferences, have palliative care consults, and enroll in hospice.***

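### Section 12.3 names no small-sample method for the primary test: if the permitted robust-variance GEE is run uncorrected with 14 hospital units, its false-positive rate is about 9-15%, not 5%

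*Combined protocol and SAP*

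**What the plan says.** Section 12.3 fixes the level: "All hypothesis tests will employ a two-sided alpha level of 0.05". For the primary outcome it offers two logistic models. One relies on "robust variance methods to account for the clustering of these data by hospital site and/or health system via generalized estimating equations (GEE"); the alternative reads "or the inclusion of a random effects terms (in which case, the results will be interpreted as cluster-specific"). The section does not choose between them. It gives no working correlation, reference distribution, variance correction or permutation test. Time is to be incorporated, in a form not stated.

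On the level of clustering, the general part of section 12.3 says "we will examine both the health system and hospital unit as clustering variables, with the hospital unit as the primary clustering variable". The primary-outcome paragraph speaks of hospital site and/or health system instead.

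Section 5 describes 14 units at two hospitals, one unit per hospital at each of seven steps, over eight periods: "we will generate a set of uniform random numbers for each of the seven clusters to be assigned to a starting period". Section 7.1 refers to about 15,000 patients "admitted to these 23* units for our primary and secondary outcomes (Aim 1"). Its footnote places 14 units in the stepped wedge and adds that "an additional 9 units (3 at BMC and 6 at NorthShore) will be used to recruit additional control participants only".

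Section 12.2 discusses the ICC, unequal cluster sizes and the surplus of records. It does not discuss how few clusters there are.

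**The concern.** The sandwich variance used in robust GEE is justified when there are many independent clusters. With few, it is biased downwards and itself variable, so a Wald statistic compared with 1.96 rejects too often. The number of patients per cluster does not cure this. An analyst following section 12.3 to the letter could therefore report a primary p-value and confidence interval at a nominal 5% level while the real error rate is two to three times that. The assurance in section 12.2 that 15,000 records are more than adequate concerns power and does not bear on this.

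**Working it through.** **Inputs from the documents.** Two-sided alpha 0.05, hospital unit as primary cluster, and time adjustment (12.3); 14 units, two per step, eight periods (5); nine further control-only units, 14 + 9 = 23 (7.1); 25% under usual care, 35% with intervention, ICC 0.01, minimum 2,394 and expected 15,000 records (12.2).

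**Assumed, because not given.** Cluster-size coefficient of variation (CV) 0 or 0.5; cluster autocorrelation 1 (no drift) or 0.8.

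**The plan's own sample size.** 440 x 2 x 2.72 = 2,393.6, so 2,394 follows from 440. The 440 itself does not match its label. With n = [z(0.975)√(2 x 0.30 x 0.70) + z(power)√(0.25 x 0.75 + 0.35 x 0.65)]² / 0.10²:
- 80% power: (1.960 x 0.648 + 0.842 x 0.644)² / 0.01 = 329 per group
- 90% power: (1.960 x 0.648 + 1.282 x 0.644)² / 0.01 = 440 per group

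The stated 440 is the 90% figure. That is conservative and does not affect the error rate examined here.

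**Null simulation.** 4,000 trials per scenario with 15,000 records, that is 15,000 / (14 x 8) = 134 per unit-period. Total between-unit variance on the probability scale is 0.01 x 0.25 x 0.75 = 0.001875, split 80:20 between unit and unit-by-period when the autocorrelation is 0.8. The model has period effects, hospital and treatment. Monte Carlo standard error is about 0.3 points near 5% and 0.5 points near 12%. The random-intercept rows use a full-likelihood fit and 3,000 trials.

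Rejection rate (%) at nominal 5%, by (CV, autocorrelation):

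| Units | Test | (0.5, 1) | (0.5, 0.8) | (0, 1) | (0, 0.8) |
|---|---|---|---|---|---|
| 14 | Robust z, independence | 15.2 | 13.8 | 12.1 | 11.8 |
| 14 | Robust z, exchangeable | 11.3 | 11.6 | 9.4 | 10.4 |
| 14 | Random unit intercept, Wald z | 5.7 | 9.1 | 5.3 | 8.9 |
| 14 | Mancl-DeRouen, t(12), exchangeable | 4.0 | 4.0 | 3.1 | 3.9 |
| 14 | Kauermann-Carroll, t(12), exchangeable | 5.5 | 6.0 | 4.6 | 5.4 |
| 14 | Permutation, 7! = 5,040 orders | 5.2 | 5.2 | 4.5 | 5.4 |
| 23 | Robust z, independence | 10.5 | 10.7 | 8.5 | 8.5 |
| 23 | Robust z, exchangeable | 8.5 | 8.6 | 8.2 | 8.2 |
| 23 | Random unit intercept, Wald z | 5.0 | 7.3 | 5.2 | 7.1 |
| 23 | Mancl-DeRouen, t(21), exchangeable | 4.7 | 4.4 | 4.4 | 4.6 |

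Relative to 5%, uncorrected GEE runs from 9.4/5 = 1.9 to 15.2/5 = 3.0 times with 14 units, and from 8.2/5 = 1.6 to 10.7/5 = 2.1 times with 23.

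**Second simulation, coded separately** (CV 0 or 0.6, ICC 0.01 or 0.05). With 14 units, uncorrected GEE gave 9.5-11.9% (exchangeable) and 9.8-14.7% (independence); with 23 units, 7.6-9.0% and 8.0-10.5%. The 14-unit rates were about the same at 2,394, 9,000 and 15,000 records. Replacing the normal reference by t(units minus 2), without correcting the variance, still left about 6-11%.

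**Why the random intercept alone can fail.** At autocorrelation 0.8 it ignores a unit-by-period component. The cell variance is understated by a factor of about 1 + (134 - 1) x 0.01 x (1 - 0.8) = 1.27, so the standard error is too small by √1.27 = 1.13. The two-sided rate is then 2[1 - Φ(1.96/1.13)], about 8%, in line with the table.

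**Health system as cluster.** With only two clusters, robust GEE rejected about 40% of null trials (1,500 trials per scenario).

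**Size of the false positives.** Points are the log odds ratio x 0.1875 (0.25 x 0.75). At ICC 0.01 the median false positive was 2.3-4.1 points and the largest in 32,000 null trials was 8.9, below the 10-point benchmark in section 12.2. At an assumed ICC of 0.05 (independence, CV 0.5, autocorrelation 0.8) the median was about 8 points, and the largest was 16.4 in one run and 22.4 in another.

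**The case against.** The strongest reply is that section 12.3 does not prescribe the faulty test. The inflation needs the GEE option, no correction and a normal reference; the text on robust variance is silent on the last two, and a competent analyst might supply them. A reader might infer that the primary test of this trial has an error rate of 9-15%. The documents do not support that. They permit such a test but also permit a mixed model, which is near nominal without drift, and no autocorrelation is given from which drift could be judged. What stands is that the plan rules nothing out, and that inflation under uncorrected GEE persists with equal units and no drift (9.4-12.1%).

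A second reply is that 23 units may enter, which softens the problem. The footnote in section 7.1 ties the nine extra units to low recruitment and the target of 600 caregivers. Aim 1 takes all eligible patients under a consent waiver (section 9), so recruitment points to the caregiver survey. The main text of section 7.1 keeps the other reading open, but 14 is the main case, and 23 units still exceed 5%.

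A third reply is that section 12.2 puts effect size above p-values. That limits the harm at ICC 0.01. It does not repair an interval that is too narrow, and it offers less protection if the ICC is larger.

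**Conclusion.** The omission is real and should be corrected before analysis. Run uncorrected with the unit as cluster, the GEE option has a false-positive rate of about 9-12% (exchangeable) or 12-15% (independence) with 14 units, and about 8-11% with 23. These figures rest on the documents' alpha, ICC, baseline rate and layout, and on assumed ranges for size variation and autocorrelation.

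Three stronger inferences are not supported:
- The 40% rate is not the planned analysis. Section 12.3 makes the unit the primary cluster; the figure shows only why the conflicting wording must be reconciled.
- The data-dependent covariate screen ("Variables found to differ between the study groups will be further evaluated to assess their confounding effects"), the open choice of effect measure and the interaction steps do not add to the rates above. They are separate prespecification points, and section 12.3 describes the interaction work as model validation and a lead for future research.
- False positives are not shown to be trivial in general. That holds at ICC 0.01 and fails at an assumed ICC of 0.05.

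**What to change.** In section 12.3, name one primary test with the hospital unit as cluster, a stated form of period adjustment and a small-sample method.
- **First choice:** exchangeable GEE with Mancl-DeRouen variance and t(units minus 2), which is 12 degrees of freedom with 14 units; or a permutation test over the 5,040 orders of the seven randomised clusters. In the second simulation Mancl-DeRouen also held under linear time (4.5-5.1%, 14 units).
- **Second choice:** Kauermann-Carroll with the same t reference, with exchangeable correlation only. It is mildly liberal with unequal units, which section 12.2 expects, and reached 7.4% in the second simulation.
- **If a mixed model is preferred:** add a unit-by-period random effect and small-sample degrees of freedom.

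Also replace the hospital site and/or health system wording with the unit, state whether the nine extra units enter the Aim 1 analysis, and make the main-effects intervention contrast the primary test whatever the interaction results.

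The cost is plan wording and standard software options. With 14 units and Mancl-DeRouen, the interval half-width goes from 2.1-2.3 to 2.8-3.1 points, or 31-35% wider. Simulated power for 25% versus 35% stays near 100% at 15,000 records and is 82-83% at 2,394 (89-90% with the permutation test). If the nine units do enter, the permutation test weakens to 70-75% at 2,394, because those units are not randomised; Mancl-DeRouen gives 92-93%.
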